5.6.2. Dose Limiting Toxicities

DLT evaluability is defined for patients in Safety cohorts as follows:

- Patient completed the first 21-day cycle (DLT assessment period of 21 days)
- Patient received all administrations of nanrilkefusp alfa during the DLT period as per schedule (± 1 day)
- Patient received cetuximab as per schedule (± 1 day)
- Patients experienced at least one DLT during the DLT assessment period, regardless of the number of nanrilkefusp alfa or cetuximab administrations during the DLT period

DLTs will be identified in the Adverse event eCRF page with “Is the adverse event a Dose Limiting Toxicity?” = “Yes”.

Patient needs to receive all administrations of nanrilkefusp alfa and cetuximab during the DLT period as planned per schedule.

The incidence of DLTs by dose level will be summarized with counts and percentages by SOC and PT in ASaT population.

A listing of all DLTs including the first and last dates of treatment will be presented for the ASaT population.

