4.1.1 Study design

First, 3 patients will be recruited sequentially so that the first administrations of nanrilkefusp alfa to the first and second patients will be 7 days apart and the second and third patients will not be dosed on the same day. These patients will be treated with cetuximab in combination with 9 µg/kg nanrilkefusp alfa, a dose one dose level below the RP2D as determined in study SC103 (AURELIO-03) which evaluated nanrilkefusp alfa at doses up to 12 µg/kg in combination with pembrolizumab. Please see section [6.1](#) for more details on administration of study interventions.

After the last patient in the 9 µg/kg safety cohort completes the first treatment cycle of 21 days, i.e., the DLT assessment period, an internal safety committee (ISC) will review the safety data.

If at least one patient in the initial 9 µg/kg safety cohort experiences a DLT, an additional 3 patients will be recruited into the 9 µg/kg safety cohort. The ISC will review the safety data of these 3 additional patients and decide whether it is safe to increase the dose to 12 µg/kg nanrilkefusp alfa in combination with cetuximab in the second safety cohort or whether the study should proceed with 9 µg/kg nanrilkefusp alfa or with 6 µg/kg nanrilkefusp alfa.

If there are no safety concerns in the initial 9 µg/kg safety cohort, the study will proceed to the second safety cohort and sequentially recruit another 3 patients who will receive 12 µg/kg nanrilkefusp alfa in combination with cetuximab. As in the 9 µg/kg cohort, the first administrations of nanrilkefusp alfa to the first and second patients will be 7 days apart and the second and third patients will not be dosed on the same day. Safety in the 12 µg/kg cohort will be evaluated by the ISC after the last patient completes the DLT assessment period (first treatment cycle of 21 days).

If at least one patient in the 12 µg/kg safety cohort experiences a DLT, an additional 3 patients will be recruited into the 12 µg/kg safety cohort. The ISC will review the safety data of these 3 additional patients and decide whether it is safe to proceed to the main cohort with patients receiving 12 µg/kg nanrilkefusp alfa in combination with cetuximab or whether the study should continue at a lower nanrilkefusp alfa dose.

If there are no safety concerns in the 12 µg/kg safety cohort, the study will proceed to the main cohort and recruit patients who will receive 12 µg/kg nanrilkefusp alfa in combination with cetuximab.

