4.1.2 DLT definition

For the safety cohorts, DLTs will be AEs listed below, specified and graded according to CTCAE, version 5.0, without consideration of causality to nanrilefusp alfa. AEs listed below will be considered DLTs unless clearly not related to nanrilefusp alfa (i.e., events clearly due to cancer, other comorbid illness, or unequivocally related to concomitant medications).

Every DLT in the study will be discussed with the study investigators and every effort will be made to ensure all clinical assessments are carried out and documented appropriately and, wherever possible, histological assessments are also performed to identify and understand the safety profile of nanrilefusp alfa in combination with cetuximab.

AEs that are considered DLTs

- All grade 5 events not clearly related to disease progression or any other causes will be considered DLTs.
- Any grade 3 or higher non-hematologic toxicity regardless of duration will be considered a DLT, with the following exceptions that are not considered DLTs:
 - Grade 3 nausea, vomiting, or diarrhea that can be controlled within 72 hours
 - Grade 3 fatigue that lasts less than 5 days
 - Grade 3 or higher correctable electrolyte abnormalities that last less than 72 hours and are not associated with clinical complications
 - Grade 3 or higher serum amylase or lipase not associated with clinical manifestations of pancreatitis
 - Grade 3 aspartate aminotransferase (AST) or alanine aminotransferase (ALT) increase or grade 3 blood bilirubin increase that lasts 5 days or less
- Hy's law cases will be considered DLTs (see section [10.3](#)).
- Hematologic DLTs will include the following:
 - Grade 4 decreased neutrophil count or decreased platelet count lasting more than 7 days
 - Febrile neutropenia
 - Grade 3 or higher decreased platelet count with bleeding

AEs that are not considered DLTs

- Inflammatory reaction attributed to a local antitumor response (grade 3 tumor pain caused by acute inflammatory reaction at tumor-bearing sites, e.g., like sites of metastatic disease or lymph nodes) that resolves to grade 1 within 3 weeks
- Concurrent vitiligo or alopecia of any CTCAE grade

Other clinically significant toxicities, including a single event or multiple occurrences of the same event, may be considered DLTs in the safety cohorts.

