9.2 Analysis sets

9.2.1 All-subjects-as-treated population

The all-subjects-as-treated (ASaT) population will consist of all patients exposed to nanrilkefusp alfa or cetuximab.

All safety analyses will be performed on the ASaT population.

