9.3.3.2 Safety endpoints

- DLTs

The incidence of DLTs (in DLT-evaluable patients, see section 4.1.3) by dose level will be summarized with counts and percentages.

- TEAEs

A TEAE is defined as an AE that started or worsened at or after the start of study treatment.

TEAEs will be summarized with counts and percentages. These will be provided for the incidence of, but not limited to: any TEAE, any serious TEAE, any grade 3-5 TEAE, any drug-related TEAE, any serious and drug-related TEAE, any grade 3-5 and drug-related TEAE, temporarily discontinued due to a TEAE, permanently discontinued due to a TEAE, death. TEAE incidence frequencies by system organ class and preferred term will also be provided.

- Safety laboratory findings and vital signs

Safety laboratory findings and vital signs measurements will be summarized accordingly (if categorical or continuous data). Laboratory results will be summarized using SI units as appropriate.

Further details on analyses to be performed will be specified in the final statistical analysis plan (SAP).

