3.3. All-Subjects-as-Treated Population

The All-Subjects-as-Treated (ASaT) population will consist of all patients exposed to nanrilkefusp alfa or cetuximab.

All safety analyses will be performed on the ASaT population. The ASaT population will also be used for selected efficacy analyses.

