5.1. General Principles

All data processing, summarization and analyses will be performed using Fortrea's SAS Environment / Version 9.4 (or later) of the SAS® statistical software package.

The analyses will be descriptive; no formal testing of statistical hypotheses is planned.

Summary statistics:

The default summary statistics for quantitative variables will be the number of observations (n), mean, Standard Deviation (SD), median, minimum (min) and maximum (max), for those patients with data. For qualitative variables, the number (n) and percentage (%) of patients with non-missing data per category will be the default summary presentation, and where appropriate and present, the number of missing values as a "Missing" category. Number of patients in the analysis population will be used as denominator for percentages calculation, unless stated otherwise in TFLs.

Time-to-event endpoints will be summarized using Kaplan-Meier (KM) method. Estimation of median time and the associated 95% Confidence Interval (CI) will be provided using log-log transformation. Number of events, number of censored patients and descriptive statistics [25th and 75th percentiles, minimum and maximum] for time-to-event endpoints will be also provided. The KM curves will be graphically displayed.

Time conversion:

The following conversion factors will be used to convert days into months or years:

1 week = 7 days, 1 month = 30.4375 days, 1 year = 365.25 days.

Laboratory data:

All laboratory clinical safety and urine test results will be received from the local laboratories, and the results will be provided in both Standard Internal (SI) and conventional units. For the TFLs, the results will be summarized or presented in International System of Units (SI) units. Refer to Appendix of the TFLs mock shells for the SI unit corresponding to each laboratory test. Biomarkers, inflammatory cytokines and PK/ADA results will be received from the central laboratories.

Tables, Figures, and Listings (TFLs):

In the listings, laboratory values converted from conventional to International System of Units (SI) units will be reported to the same precision as values originally recorded as SI. Derived values for change/ percent changes in target lesions, and all safety endpoints will be rounded with one decimal place.

Refer to Appendix of the TFL shells for the precision level in which each laboratory test is reported by the central laboratories.

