5.9. Biomarkers

Biomarker collection data from eCRF will be listed for screened population. Biomarkers results will be reported separately for the CSR.

6. Changes in the Conduct of the Study or Planned Analysis

The following changes or precisions from protocol specified statistical analyses are made in this SAP.

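### SAP 5.6.2 reports DLT incidence in all treated patients, not in the DLT-evaluable patients the protocol specifies, and does not declare the change

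*SAP*

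**What the plan says.** Protocol 9.3.3.2 sets the rule for this endpoint: "The incidence of DLTs (in DLT-evaluable patients, see section 4.1.3) by dose level will be summarized with counts and percentages". Protocol 4.1.2 limits DLTs to the run-in: "For the safety cohorts, DLTs will be AEs listed below, specified and graded according to CTCAE, version 5.0". SAP 5.6.2 likewise defines DLT evaluability only for safety-cohort patients. It then specifies the table differently: "The incidence of DLTs by dose level will be summarized with counts and percentages by SOC and PT in ASaT population".

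SAP 3.3 defines that population: "The All-Subjects-as-Treated (ASaT) population will consist of all patients exposed to nanrilkefusp alfa or cetuximab". SAP 5.1 gives the default for percentages: "Number of patients in the analysis population will be used as denominator for percentages calculation, unless stated otherwise in TFLs". A general sentence in Protocol 9.2.1 points the same way as the SAP: "All safety analyses will be performed on the ASaT population".

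SAP section 6 opens with "The following changes or precisions from protocol specified statistical analyses are made in this SAP" and then lists three items: the SD/iSD derivation, duration of follow-up and PK parameters. The DLT population is not among them. SAP section 3 defines no DLT-evaluable set, and the disposition summary in SAP 5.2 does not count one.

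**The concern.** DLTs are the endpoint for the secondary objective of determining the recommended phase 2 dose of the combination. A DLT percentage is meaningful only among patients who were assessed for DLTs. With ASaT as the denominator, every main-cohort patient at a dose level lowers that level's percentage, because no DLT is defined for them and they cannot add to the numerator. The same toxicity in the same run-in cohort would then be reported as a different rate depending on how many patients were enrolled later. It would also not be the rate the protocol promises.

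A second problem concerns who is evaluable. SAP 5.6.2 lists four evaluability bullets with no 'or' between them. The fourth counts a patient with a DLT whatever doses were received. Read as joint conditions, the four bullets would make only patients with a DLT evaluable. A later sentence in the same section requires all administrations, which contradicts the fourth bullet. Protocol 4.1.3 has no exception for a patient whose dosing was stopped by a DLT, although the replacement rule in Protocol 4.1.1 implies that such patients are kept.

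**Working it through.** **Inputs**

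- Total sample 52, including the safety cohorts; 3 to 6 DLT-evaluable patients per dose level; 6 to 12 in the safety cohorts (Protocol 9.5, SAP 2.3).
- Main cohort approximately 46 (Protocol 1.2).
- If at least one patient in a safety cohort "experiences a DLT, an additional 3 patients will be recruited into the" same cohort, so a 12 µg/kg cohort with a DLT has 3 + 3 = 6 patients (Protocol 4.1.1).
- If 12 µg/kg is cleared, the main cohort receives 12 µg/kg (Protocol 4.1.1).
- Futility look at N = 16 (Protocol 9.4).

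**The plan's own figures.** 46 + 3 + 3 = 52, as stated. Two dose levels of 3 to 6 patients give 6 to 12, as stated.

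**Protocol rate.** DLT patients / DLT-evaluable patients = 1/6 = 16.7% (exact 95% CI 0.4% to 64.1%).

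**SAP rate.** DLT patients / ASaT patients at that dose level = 1/n, an understatement by a factor of n/6.

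| Main cohort at 12 µg/kg | n at 12 µg/kg | 1/n | n/6 |
|---|---|---|---|
| 52 in total, 6 of them at 9 µg/kg | 52 − 6 = 46 | 2.17% | 7.67 |
| 52 in total, 3 of them at 9 µg/kg | 52 − 3 = 49 | 2.04% | 8.17 |
| 46 in the main cohort plus 6 in the safety cohort | 46 + 6 = 52 | 1.92% | 8.67 |
| Stop at 16, 6 of them at 9 µg/kg | 16 − 6 = 10 | 10.0% | 1.67 |
| Stop at 16, 3 of them at 9 µg/kg | 16 − 3 = 13 | 7.69% | 2.17 |

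The rate falls steadily with enrolment. With m main-cohort patients at 12 µg/kg it is 1/(6 + m):

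- m = 0: 16.7%
- m = 10: 1/16 = 6.3%
- m = 20: 1/26 = 3.8%
- m = 43: 1/49 = 2.0%

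The 52 and the 16 count patients in the efficacy population. ASaT is at least as large, so for each row based on those counts the percentage is an upper value and the factor a lower one.

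**The case against.** **Protocol 9.2.1 puts all safety analyses in ASaT, and DLTs are listed as a safety endpoint.** The protocol does contain both rules and states no order of precedence. But the sentence in 9.3.3.2 is specific to this endpoint and names its denominator. Applying the general rule would leave that wording without effect. If the SAP chose the general rule, it should have said so in section 6.

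**The table shells may set another denominator.** SAP 5.1 allows this, and the shells are not part of the protocol or SAP. This stands as a condition on the size, not on the mismatch in the text. A shell limited to safety-cohort patients would still not fully restore the protocol rate, because non-evaluable patients who were replaced remain in ASaT.

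**The 16.7% depends on how evaluability is read.** Under a literal Protocol 4.1.3, a patient whose doses were stopped by a DLT is not evaluable, and the protocol rate would be 0/5 = 0%. The 1/6 also needs all six patients to be evaluable, whereas Protocol 4.1.1 guarantees replacement only up to at least three per cohort. Both conditions are real. The first is itself the evaluability defect described above, since a definition that removes DLT cases from a DLT rate cannot be intended.

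**The consequence is limited.** This stands. The internal safety committee does not use this table to decide dose. Counts are shown, each DLT is listed, and a rate from six patients is imprecise in any case. With no DLTs, both denominators give 0%.

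**Conclusion.** The concern holds. The SAP changes the denominator of a named secondary endpoint from the one in Protocol 9.3.3.2 and does not declare the change. With one DLT at 12 µg/kg, the reported rate would be 1.9% to 2.2% instead of 16.7% if the trial enrols fully. It would be at most 7.7% to 10.0% if the trial stops at the 16-patient look, an understatement of at least 1.7 to 2.2 times.

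These figures assume that:

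- the main cohort runs at 12 µg/kg;
- all six patients in the expanded 12 µg/kg cohort are evaluable, including the one with the DLT;
- the table shells do not override SAP 5.1.

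If the main cohort runs at 9 µg/kg, the dilution falls on the 9 µg/kg row and the 12 µg/kg rate is not diluted. The harm is to the reported rate, not to escalation, so this should be fixed but does not threaten the conduct of the trial.

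**What to change.** In SAP 5.6.2, define a DLT-evaluable set: safety-cohort patients who **either** had a DLT in the 21-day assessment period **or** meet the three completion and dosing criteria. Use it, by safety-cohort dose level, as the denominator for DLT incidence in place of ASaT. The DLT listing can stay in ASaT. Delete the sentence requiring all administrations, which contradicts the fourth bullet. Bring the evaluability wording in Protocol 4.1.1, 4.1.3 and 9.3.3.2 and SAP 5.6.2 into line.

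If ASaT is kept on purpose, declare and justify it in SAP section 6 and show the DLT-evaluable rate beside it.

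The cost is SAP wording and one population flag, with no new data. Clarifying Protocol 4.1.3 may need submission under Protocol 10.1.1, but the SAP change stands alone and the clarification can wait for a later amendment.

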5.6.3. Adverse Events

All AEs recorded on the eCRF will be coded using the MedDRA dictionary [most recent version at time of DB lock] and classified as either pre-treatment AEs or treatment-emergent AEs (TEAEs) as follows:

- CRS symptoms will not be considered in the analysis to avoid duplication, as the diagnosis is reported instead.
- Pre-treatment AEs are events that start prior to the start of the study treatment.
- A TEAE is defined as an AE that started or worsened at or after the start of study treatment.
- Treatment-Emergent Serious AEs (TESAEs) will be defined as TEAEs deemed by the investigator as Serious = “Yes”.
- The relationship between a TEAE and nanrilkefusp alfa treatment is assessed as suspected or not suspected (same with cetuximab). A nanrilkefusp alfa treatment-related TEAE will be defined as a TEAE considered by the investigator as suspected. A cetuximab-related TEAE will be defined as a TEAE considered by the investigator as suspected.
- Assessment of AE severity/intensity will be based on the NCI-CTCAE (version 5.0). Severe TEAEs are defined as TEAEs assessed as being “Severe (=Grade 3)/ Grade 4/Grade 5” in intensity.
- TEAEs leading to dose reduction of nanrilkefusp alfa treatment are defined as TEAEs where “Dose reduced” is indicated as “Yes”.
- TEAEs leading to temporary discontinuation of nanrilkefusp alfa treatment are defined as TEAEs where “Temporarily discontinued” is indicated as “Yes”.
- TEAEs leading to permanent discontinuation of nanrilkefusp alfa treatment are defined as TEAEs where “Permanently discontinued” is indicated as “Yes”.
- TEAEs leading to dose reduction of cetuximab treatment are defined as TEAEs where “Dose reduced” is indicated as “Yes”.
- TEAEs leading to temporary discontinuation of cetuximab treatment are defined as TEAEs where “Temporarily discontinued” is indicated as “Yes”.
- TEAEs leading to permanent discontinuation of cetuximab treatment are defined as TEAEs where “Permanently discontinued” is indicated as “Yes”.

According to the eCRF, if a patient has (for example) 2 episodes of a same AE but a change in intensity, they will be identified using the 2 following CRF items:

- Is this a change in severity of an already existing AE equals to “Yes”
- If Yes, AE identifier.

In that case, to derive the TEAE flag, the AE identified/linked with the items above will be considered as the same “linked” AE but with 2 episodes. Thus, if worsening or both TEAE, the linked AE (both episodes) will be flagged as the TEAE.

Linked AEs will be selected for analysis in tables based on their worst case scenario attribute e.g. maximum CTC grade, causal relationship, seriousness, treatment emergence and action taken out of all records.

The ordering (the worst to best) for the following characteristics will be applied:

- Action taken: permanently discontinued, temporarily discontinued, dose reduced, other action, no action taken.
- Relationship: suspected, not suspected.
- Toxicity Grade: Grade 5 to Grade 1.

AE records within a linked AE can be given different treatment-emergence status. Treatment emergence for linked AEs will be established as those records in the linked AE with a worsening of severity from the preceding record.

Adverse events will be summarized by default descriptive summary statistics for categorical variables for the ASaT population by overall as follows:

Combination treatment related is defined as being related to either nanrilkefusp alfa or cetuximab (or both), and discontinuation of combination treatment means discontinuation of either nanrilkefusp alfa or cetuximab (or both).

- An overview of TEAEs including the number and percentage of patients with at least one of each mentioned TEAE type:
 - Any TEAE
 - Leading to dose reduction of nanrilkefusp alfa
 - Leading to temporary discontinuation of nanrilkefusp alfa
 - Leading to dose reduction and temporary discontinuation of nanrilkefusp alfa.
 - Leading to permanent discontinuation of nanrilkefusp alfa
 - Leading to permanent discontinuation of combination treatment
 - Serious
 - Grade 1 severity (mild)
 - Grade 2 severity (moderate)
 - Grade 3 severity (severe)
 - Grade 4 severity (life-threatening or disabling)
 - Grade 5 severity (death related to TEAE)
 - \geq Grade 3 severity (severe, life-threatening, disabling, death related to TEAE)
 - Any nanrilkefusp alfa-related TEAE
 - Leading to permanent discontinuation of nanrilkefusp alfa
 - Leading to permanent discontinuation of combination treatment.
 - Serious

- Grade 1 severity (mild)
- Grade 2 severity (moderate)
- Grade 3 severity (severe)
- Grade 4 severity (life-threatening or disabling)
- Grade 5 severity (death related to TEAE)
- \geq Grade 3 severity (severe, life-threatening, disabling, death related to TEAE)
- Any combination-related TEAE
 - Leading to permanent discontinuation of combination treatment
 - Serious
 - Grade 1 severity (mild)
 - Grade 2 severity (moderate)
 - Grade 3 severity (severe)
 - Grade 4 severity (life-threatening or disabling)
 - Grade 5 severity (death related to TEAE)
 - \geq Grade 3 severity (severe, life-threatening, disabling, death related to TEAE)
- The number and percentage of patients reporting each TEAE and the count of number of events will be summarized by SOC and PT for the following types of TEAEs in the ASaT population:
 - TEAEs
 - TEAEs occurring in \geq 5% of patients
 - TEAEs leading to dose reduction of nanrilkefusp alfa
 - TEAEs leading to temporary discontinuation of nanrilkefusp alfa
 - TEAEs leading to dose reduction and temporary discontinuation of nanrilkefusp alfa
 - TEAEs leading to permanent discontinuation of nanrilkefusp alfa
 - TEAEs leading to temporary discontinuation of cetuximab
 - TEAEs leading to permanent discontinuation of cetuximab
 - TEAEs leading to permanent discontinuation of combination treatment
 - TEAEs leading to death
 - Serious TEAEs
 - Non-serious TEAEs occurring in \geq 5% of patients
 - TEAEs with \geq Grade 3 severity
 - TEAEs with \geq Grade 3 severity occurring in \geq 5% of patients
 - TEAEs by maximum severity grade
 - nanrilkefusp alfa-related TEAEs
 - nanrilkefusp alfa-related TEAEs leading to permanent discontinuation of nanrilkefusp alfa
 - nanrilkefusp alfa-related TEAEs leading to death
 - Serious nanrilkefusp alfa-related TEAEs
 - nanrilkefusp alfa-related TEAEs with \geq Grade 3 severity
 - nanrilkefusp alfa-related TEAEs by maximum severity grade

- Combination-treatment-related TEAEs
- Combination-treatment-related TEAEs leading to death
- Serious combination-treatment-related TEAEs
- Combination-treatment-related TEAEs with \geq Grade 3 severity
- Combination-treatment-related TEAEs by maximum severity grade

- The number and percentage of patients reporting each TEAE and the count of number of events will be summarized by PT for the following types of TEAEs:
 - TEAEs
 - TEAEs occurring in $\geq 5\%$ of patients
 - nanrilkefusp alfa-related TEAEs
 - Combination-treatment-related TEAEs
 - Serious TEAEs
 - Serious nanrilkefusp alfa-related TEAEs
 - Serious combination-treatment-related TEAEs
- The number and percentage of patients who died will be summarized by the primary and secondary reason of death in the enrolled population.

In the above summaries, patients with more than one TEAE within a particular SOC are counted only once for that SOC. Similarly, patients with more than one TEAE within a particular PT are counted only once for that PT.

For summaries by maximum severity, patients with multiple TEAEs within a particular SOC or PT will be counted under the category of their most severe TEAE within that SOC or PT.

Summaries by SOCs and PTs will be sorted by SOCs by their descending Order (MedDRA) and PTs within SOC by descending order of total incidence. Where preferred terms tie PTs will be sorted alphabetically.

All AE data will be listed and Pre-treatment AEs and TEAEs will be presented together. Treatment-emergence status will be flagged in the listing. The listing will present the relative start and stop day of the AE calculated relative to the first dose of treatment and will be presented for those patients who received at least one dose of treatment. If the AE is "Ongoing" it will be indicated as such in the listing and the relative stop day will not be calculated. Only original dates will be presented in the listing even though the relative day may be based on an imputed date.

In addition, the following listings will be presented:

- Listing of deaths
- Listing of AEs
- Listing of serious TEAEs
- Listing of TEAEs leading to temporary discontinuation of nanrilkefusp alfa

- Listing of TEAEs leading to dose reduction of nanrilkefusp alfa
- Listing of TEAEs leading to permanent discontinuation of cetuximab

TEAE occurring in $\geq 10\%$ of patients will be presented graphically for ASaT population.

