6.5 Dose modification and toxicity management

6.5.1 Dose modification and toxicity management for nanrilefusp alfa

Dose modification and toxicity management for nanrilefusp alfa for safety reasons, will be discussed on a case-by-case basis between the site and the sponsor's medical monitor. Recommendations for clinical management of cytokine release syndrome are provided in [Table 6.4](#).

To minimize the risk for injection site reaction, subcutaneous injection sites should be rotated to different areas of the body (upper and lower extremities, each of the 4 quadrants of the abdomen) to minimize the summated local effects of nanrilefusp alfa administration.

To minimize the risks associated with shortening of the QT interval, vital signs and electrocardiography (ECG) must be closely monitored as per Protocol and institutional guidelines.

Liver function tests for nanrilefusp alfa toxicity evaluation in this study will include AST, ALT, total bilirubin, and alkaline phosphatase.

Nanrilefusp alfa-related hepatic toxicities should be managed as shown in [Table 6.2](#).

Table 6.2: Management of nanrilkefusp alfa-related hepatic toxicities

Nanrilkefusp alfa-related hepatic toxicity	Severity	Nanrilkefusp alfa dose modification
AST increased or ALT increased, or blood bilirubin increased	Grade 2 with AST or ALT >3 to $\leq 5 \times \text{ULN}$ or total bilirubin >1.5 to $\leq 3 \times \text{ULN}$	Withhold nanrilkefusp alfa Resume nanrilkefusp alfa if increased values return to grade ≤ 1
	Grade ≥ 3 with AST or ALT $>5 \times \text{ULN}$ or total bilirubin $>3 \times \text{ULN}$	Withhold nanrilkefusp alfa Resume nanrilkefusp alfa at one dose level below or reduce by 3 $\mu\text{g}/\text{kg}$ if increased values return to grade ≤ 1 Permanently discontinue nanrilkefusp alfa on second occurrence of grade ≥ 3 hepatic event

Please also refer to the IB, section 6.6 (Management guidelines for identified and potential risks).

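### SAP 5.6.3 gives two incompatible treatment-emergence rules for linked AEs, takes worst-case attributes over all records and keeps only one action, so several TEAE counts depend on the programmer's reading

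*SAP*

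**What the plan says.** All of this is in SAP 5.6.3 unless stated otherwise.

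- **General definition.** "A TEAE is defined as an AE that started or worsened at or after the start of study treatment". Protocol 9.3.3.2 has the same definition.
- **What creates a linked AE.** An eCRF item marks a record as a change in severity of an existing AE. The item gives no direction, so an improvement creates a linked record too.
- **Whole-event rule.** "Thus, if worsening or both TEAE, the linked AE (both episodes) will be flagged as the TEAE".
- **Record rule.** "AE records within a linked AE can be given different treatment-emergence status", followed by "Treatment emergence for linked AEs will be established as those records in the linked AE with a worsening of severity from the preceding record".
- **Selection for tables.** "Linked AEs will be selected for analysis in tables based on their worst case scenario attribute", with the examples "maximum CTC grade, causal relationship, seriousness, treatment emergence and action taken out of all records".
- **Action taken.** Actions are ranked from worst to best, with dose reduction below both permanent and temporary discontinuation. Earlier in the same section, dose reduction, temporary discontinuation and permanent discontinuation are each defined by their own Yes item, separately for each drug. The planned outputs include a table of TEAEs leading to both dose reduction and temporary discontinuation of nanrilkefusp alfa.

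**The concern.** Type, frequency and severity of TEAEs is a secondary endpoint, and in a single-arm study these tables carry the safety result. Three features leave the counts open.

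1. The whole-event rule gives every record of a linked AE one status, while the record rule lets records differ. The SAP does not say which prevails. The record rule also drops the word started from the general definition, is not tied to first dose, and cannot classify an onset record, which has no preceding record.
2. Grade, causality and seriousness are taken from all records of the linked AE, including those before first dose.
3. A single ranked action cannot represent a linked AE that led to both an interruption and a reduction, yet a planned table needs both.

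The events exposed to the first problem are those that begin on treatment at their highest grade and then improve.

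**Working it through.** The plan gives no figure to reproduce. The check applies the rules to every possible grade sequence, using grades 1 to 4, a change of grade at each step, and at least one record on treatment. The results count patterns and are not expected frequencies.

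**Number of patterns**
- Two records: 4 × 3 = 12 sequences, each with 0 or 1 pre-dose record, so 12 × 2 = 24.
- Three records: 4 × 3 × 3 = 36 sequences, each with 0, 1 or 2 pre-dose records, so 36 × 3 = 108.

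The reference is the general definition: the AE started on treatment, or a record on treatment is worse than the one before it. The whole-event rule is extended to three records as any worsening, or all records on treatment.

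**Two records**
- The two rules give different TEAE results in 6 of 24 patterns. These are the 6 falling pairs (2-1, 3-1, 3-2, 4-1, 4-2, 4-3) with onset on treatment. The whole-event rule counts them; the record rule counts none.
- Five of the 6 (all but 2-1) also leave the grade 3 or higher table under the record rule.
- In the other 24 − 6 = 18 patterns the table result is the same, because emergence is itself a worst-case attribute and one emergent record is enough.
- The whole-event rule agrees with the general definition in 24 of 24.

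**Three records**
- The rules differ in 4 of 108 patterns: the strictly falling sequences 3-2-1, 4-2-1, 4-3-1 and 4-3-2 with onset on treatment.
- The whole-event rule departs from the general definition in 14. Here the grade rises and then falls, and the rise lies wholly before first dose. With a middle grade of 2, 3 or 4 there are 1 × 1 + 2 × 2 + 3 × 3 = 14 such patterns. The record rule makes the same 14 errors and adds the 4 above, giving 18.
- Using the maximum grade over all records gives a different grade 3 or higher result from using emergent records in 17 patterns. Thirteen are the untimed-worsening cases just described (14 less 1-2-1, which never reaches grade 3). The other 17 − 13 = 4 come from the all-records maximum alone: 3-1-2 and 4-1-2, each with one or two pre-dose records. An example is grade 3 then grade 1 before first dose, followed by grade 2 on treatment, which is tabulated as a grade 3 TEAE.

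**Action taken, two records, five actions**
- Ordered pairs containing a dose reduction: 5 × 5 − 4 × 4 = 9.
- Pairs that lose it under the single-worst ranking: dose reduction with temporary or permanent discontinuation, in either order, 2 × 2 = 4. The ranking keeps 9 − 4 = 5; separate flags keep all 9.
- A reduction on one record and an interruption on another can never reach the combined table.
- The pattern is foreseeable. For nanrilkefusp alfa-related hepatic events of grade 3 or higher, Protocol Table 6.2 has the drug withheld and then: "Resume nanrilkefusp alfa at one dose level below or reduce by 3" µg/kg, once values return to grade 1 or below. If the site enters the improvement as a linked record, this is also the falling sequence that the record rule misses.

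**The case against.** The strongest reply is that a careful programmer would get most of this right. The whole-event rule is conditional, and its condition that both episodes be TEAEs rescues the AE that starts on treatment at grade 3 and improves. That event is lost only if the record rule is read literally against the general definition. SAP 5.6.3 describes two episodes, and there the whole-event rule is always right. The all-records error needs three records when the grades follow that rule, and the clearest example puts two of them inside a screening period of at most 21 days. The separate Yes items and the combined table suggest that both actions were meant to be retained. Analyses are descriptive, and all AEs are listed with their treatment-emergence flag, so a misclassification can be traced.

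Most of this stands, and it rules out some stronger readings. A reader might infer that the tables will come out wrong, or that both rules fail for AEs that start on treatment and improve; the documents support neither. A reader might also infer that a pre-dose action on study drug could be carried into a TEAE, but no such action can precede the first dose. The loss of dose reductions follows only if the ranking overrides the Yes items, and the SAP does not say that it does.

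The reply does not show which emergence sentence governs, or which of the ranking and the Yes items prevails. Nor does it remove the instruction to take attributes from all records.

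**Conclusion.** The point holds as a defect of specification. The two emergence rules are incompatible at record level, and the record rule taken literally contradicts the plan's own TEAE definition. Worst-case selection over all records can import a pre-dose grade, and the single-action ranking conflicts with the separate action items and with a planned table. The TEAE, grade 3 or higher and dose-reduction counts therefore depend on which sentence is programmed.

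The size in patients cannot be computed. It depends on how often AEs change grade and on whether sites record improvements as linked entries, and the documents give neither. A reader might infer that each affected patient shifts a table by 1/52 = 1.9 points. The documents do not support that: 52 is the target for the efficacy population, whereas the safety tables use the ASaT population, which includes anyone exposed to either drug. Patients are also counted once per system organ class and preferred term, so an affected event moves a count only when the patient has no other qualifying event there.

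The change should be made before the AE tables are produced.

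**What to change.** Replace both emergence sentences with one timed, record-level rule:

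- A record is treatment-emergent if the linked AE started at or after first dose, or if the record itself begins at or after first dose and its grade exceeds the last pre-dose grade of that linked AE. The timing condition on the record matters: without it, the pre-dose grade 3 in the sequence 3-1-2 would still qualify.
- A linked AE is a TEAE if any of its records is emergent.
- Take worst-case grade, causality and seriousness from emergent records only.
- Derive dose reduction, temporary discontinuation and permanent discontinuation each as a yes/no flag over the emergent records, per drug, in place of the single worst action.

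The sponsor should confirm one consequence. Comparing with the last pre-dose grade means that an AE which improves on treatment and then returns to no more than its pre-dose grade is not counted. That covers 10 of the 108 three-record patterns, those with one pre-dose record: 1 starting at grade 2 (2-1-2), 3 at grade 3 (3-1-2, 3-1-3, 3-2-3) and 6 at grade 4 (4-1-2, 4-1-3, 4-1-4, 4-2-3, 4-2-4, 4-3-4). If worsening is instead meant relative to the preceding record, the SAP should say so, and should still require the worsening to occur on treatment and judge the onset record by the general definition.

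The cost is one SAP paragraph and the AE derivation program. No new data are needed.
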